**1.0 Objectives / Specific Aims**

The aim of this pilot project is to collect preliminary data on the feasibility, acceptance, and efficacy of an SLP-administered psychosocial intervention for people with post-stroke aphasia. The main objective of this pilot project is to determine whether the intervention is feasible and acceptable to participants with aphasia and their care partners, and we predict that it will be. Regarding the efficacy of intervention itself, we hypothesize that the psychosocial intervention will result in lower levels of psychosocial impairment (e.g., symptoms of anxiety and depression, chronic stress), better quality of life, and better retention and adherence to rehabilitation activities (i.e., attending therapies).

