**Intervention Session 1:** Session 1 will last approximately 30 minutes and focus on psychoeducation and an introduction to behavioral activation therapy. Session agenda:

- **Assessments (5 minutes):**
  - Hospital Anxiety and Depression Scale (HADS; Zigmond & Snaith, 1983)
  - Dynamic Visual Analog Mood Scale (D-VAMS; [http://dvams.com/dvams/menu\\_home\\_dvams.htm](http://dvams.com/dvams/menu_home_dvams.htm); Barrows, 2013)
  - Simple Aphasia Stress Scale (SASS; Laures-Gore & Rice, 2019)
- Participants will receive psychoeducation focused on (10 minutes):
  - normalizing the participant's psychosocial symptoms (e.g., loss of identity, depression, anxiety) and emotions (e.g., grief, anger, guilt, fear, embarrassment, etc.), which are common after stroke.
  - Discuss common effects of stroke/aphasia on daily life (e.g., social isolation, relationships, work, daily activities).
  - Discuss ways that depression, anxiety, or low mood can affect rehabilitation (e.g., attendance, homework completion, low engagement/motivation, perhaps less neuroplasticity)
- Participants will be introduced to the concept of behavioral activation therapy and the goal to increase the number of enjoyable activities that the participant partakes in. Participants will be asked what types of activities they enjoyed before their stroke, the activities/roles in their lives that they value, and the barriers they've faced to engaging in these activities. A list will be started of activities they enjoy/value and used throughout the intervention. (15 minutes)
- **Homework:** activity monitoring for participants to track how they currently spend their time and their mood during each activity with the help of a care partner if available.

**Intervention Session 2:** This session will last about 35 minutes and will consist of ongoing behavioral activation therapy and education on sleep hygiene.

- Assessments: HADS, D-VAMS, SASS (5 minutes)
- The SLP will go over the activity monitoring assignment with the participant and schedule valued/prefereed activities with the participant for the following week. Participants and the SLP will collaboratively problem solve as concerns about ability to engage in preferred activities arise. (20 minutes)
- The SLP will educate the participant on the importance of sleep and sleep hygiene practices that can improve sleep. The SLP will suggest ways the participant can instill proper sleep hygiene into their routine. (10 minutes)

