### Secondary Outcomes:

Secondary measures of psychosocial functioning that are specifically validated for the aphasia population will be administered as well, including the D-VAMS, SASS, Stroke Aphasia Depression Questionnaire-10 (SADQ-10; Sutcliffe & Lincoln, 1998), Behavioural Outcomes of Anxiety Scale (BOA; Kneebone et al., 2012; Linley-Adams et al., 2014, Modified Perceived Stress Scale (mPSS; Hunting Pompon et al., 2018), Stroke Aphasia Quality of Life (SAQOL-39; Hilari et al., 2003), and Communication Confidence Rating Scale for Aphasia (CCRSA; Cherney et al., 2011; Babbitt et al., 2011). Most of these will be administered at baseline, post-treatment, and at 1-month follow-up (see below for a table with the timepoints for each measure and the rationale for inclusion). Two of these outcome measures will be also administered at the weekly sessions, including the D-VAMS and SASS.

A questionnaire related to attendance, retention and adherence to outpatient speech therapy services will also be collected at post-treatment to gather preliminary data on whether the psychosocial intervention was associated with good retention/in/adherence to rehabilitation activities. This will be done by administering a questionnaire to participants asking questions about whether they are receiving rehabilitation therapy, and if so, whether they have been attending and following recommendations.

Qualitative interviews will also be conducted at post-treatment and 1-month follow-up to aid in intervention refinement as well. Care partners of participants (e.g., family, friends, spouse) will be invited to participate in the interviews as well.

Table 1. Study Measures

Test Name	Construct	Timepoints	Justification
Primary			
Hospital Anxiety and Depression Scale (HADS)	Measures presence of signs/symptoms of depression and anxiety	All sessions	Overall assessment of psychosocial functioning
Secondary			
Dynamic Visual Analog Mood Scale (D-VAMS)	Measures mood based on reported feelings for 7 scales of emotion	All sessions	A weekly measure of mood fluctuations throughout the study
Simple Aphasia Stress Scale (SASS)	Measures perception of current stress level	All sessions	A weekly measure of acute stress

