Stroke Aphasia Depression Questionnaire-10 (SADQ-10)	Measures presence of signs/symptoms of depression in people with aphasia	Screening/Baseline, Post-treatment (Session 6), 1-month follow-up (Session 7)	Aphasia-validated measure of depression to compare with HADS outcome
Behavioural Outcomes of Anxiety Scale	Measures presence of signs/symptoms of anxiety	Screening/Baseline, Post-treatment (Session 6), 1-month follow-up (Session 7)	Aphasia-validated measure of anxiety to compare with HADS outcome
Modified Perceived Stress Scale (mPSS)	Measures perceived levels of stress in people with aphasia	Screening/Baseline, Post-treatment (Session 6), 1-month follow-up (Session 7)	Aphasia-validated measure of chronic stress to compare with other measures of psychosocial functioning

Stroke Aphasia Quality of Life (SAQOL-39)	Measures overall quality of life in people with aphasia	Screening/Baseline, Post-treatment (Session 6), 1-month follow-up (Session 7)	Aphasia-validated measure to examine whether intervention has an effect on quality of life
The Communication Confidence Rating Scale for Aphasia (CCRSA)	Measures how confident people with aphasia are at communicating in a range of scenarios	Screening/Baseline, Post-treatment (Session 6), 1-month follow-up (Session 7)	Aphasia-validated measure to examine whether intervention has an effect on communication confidence
Other Standardized Assessments			
Western Aphasia Battery-Revised (WAB-R)	Measures language abilities	Screening/Baseline	To determine eligibility for study and acquire language profile
Cognitive Assessment Scale for Stroke Patients	Measure cognitive abilities	Screening/Baseline	To examine relationships between cognition and primary/secondary outcome measures
Qualitative Assessments			
Rehabilitation Retention & Adherence	Measure whether they have been participating in rehabilitation activities and adhering to recommendations	Post-treatment (Session 6)	To determine whether psychosocial intervention may have had positive impact on rehabilitation retention/adherence
Participant and Care Partner Acceptability of Psychosocial Intervention	Measure participant and care partners' perceptions about psychosocial intervention	Post-treatment (Session 6), 1-month follow-up (Session 7)	To identify acceptability of the intervention by participants and their care partners and to refine intervention to meet patient needs

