### ***Inclusion Criteria***

- 18-81 years old

- Native English speaker (English fluency by age 7)
- Aphasia as a result of a left-hemisphere ischemic or hemorrhagic stroke (WAB-R Aphasia Quotient < 93.8)
- At least 1-month post-stroke
- Confirmation of left hemisphere stroke per medical records
- Discharged from hospital
- Participant is willing and able to consent for themselves.

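### The plan hypothesizes better retention and adherence to rehabilitation but records them once, at Session 6, with no matching baseline and no before-after comparison

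*Combined protocol and SAP*

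**What the plan says.** **The hypothesis.** Section 1.0 puts feasibility and acceptability first: "The main objective of this pilot project is to determine whether the intervention is feasible and acceptable". It then hypothesizes lower psychosocial impairment, improved quality of life, and "better retention and adherence to rehabilitation activities (i.e., attending therapies").

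**The stated purpose elsewhere.** Section 4.0 is the most cautious place and seeks "preliminary data on whether the psychosocial intervention was associated with good retention/in/adherence to rehabilitation activities". The rationale in Table 1 is "To determine whether psychosocial intervention may have had positive impact on rehabilitation retention/adherence". Section 10.0 speaks of efficacy in improving retention and adherence to speech therapy, and gives the questionnaire and interviews the purpose of assessing effects on it.

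**The measurement.** Section 4.0 states: "A questionnaire related to attendance, retention and adherence to outpatient speech therapy services will also be collected at post-treatment". It describes the content as "asking questions about whether they are receiving rehabilitation therapy, and if so, whether they have been attending and following recommendations". The Session 6 text in Section 10.0 narrows this to speech therapy while in the study: enrolment, attendance and home programme.

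**The status of the item.** Table 1 places it under the qualitative assessments, Section 10.0 calls it qualitative data, and Section 12.0 analyses it descriptively and for themes.

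**The concern.** *Better* is a comparative word, and so are *improving* and *effects on*. Each needs a reference level, either the same participants earlier or a comparison group. The study describes itself as a within-subject before-after design, and every other outcome named in the Section 1.0 hypothesis has a baseline measurement. Retention and adherence is the one hypothesized outcome without it.

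At stake is whether the pilot can say anything about this part of its own hypothesis. On the items as described, a participant who attended therapy reliably before the study and continued to do so would give the same Session 6 answers as one who began attending reliably because of the intervention. A good result could then be read as improvement when it only describes how participants behaved while enrolled.

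**Working it through.** The documents give no rate, effect size or power figure for retention or adherence, so there is no figure of the plan's to reproduce. The check is to trace the measurement through the documents.

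**Step 1: what the hypothesis needs.** For each participant in therapy, change = level during participation − level before the intervention. Both terms are required, or a comparison group in place of the second.

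**Step 2: what is scheduled.**

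| Place | Retention/adherence questionnaire |
|---|---|
| Section 4.0, Secondary Outcomes | Post-treatment |
| Table 1 | Post-treatment (Session 6) only |
| Section 10.0, Screening/Baseline list | Not listed; the nearest item is speech therapy history in the intake questionnaire |
| Section 10.0, Session 6 | Listed; covers therapy while in the study |
| Section 10.0, Session 7 list | Not listed |
| Table 2 | Session 6 only |
| Section 12.0 | Descriptive and qualitative analysis; no before-after comparison |

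Count of time points: baseline 0 + Session 6 1 + Session 7 0 = 1. Comparison groups: 0. By contrast, the SADQ-10, BOA, mPSS and SAQOL-39 each have 1 + 1 + 1 = 3 time points, and the HADS is given at all 8 sessions.

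**Step 3: what can be formed.** The first term in Step 1 is collected, as a retrospective self-report. The second is not described anywhere, so the difference cannot be formed for any participant.

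**Step 4: what the interviews add.** Section 10.0 assigns them the purpose of assessing effects on retention and adherence, so perceived change could come up. The topics listed for Session 6, however, are feasibility, opinions of the intervention and wanted content. Any such report would be retrospective, and Session 1 asks the clinician to "Discuss ways that depression, anxiety, or low mood can affect rehabilitation (e.g., attendance, homework completion, low engagement/motivation, perhaps less neuroplasticity"). That discussion may colour later answers.

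**Step 5: the period covered.** In Table 2, Session 1 is in week 1 and Session 6 in week 5, nominally 5 − 1 = 4 weeks. Session 1 also waits for medical records, with no maximum wait stated. The window is therefore not fixed, and a matching baseline question would need its own stated look-back period.

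**Step 6: how many can contribute.** The target is 10 completers. Eligibility requires "At least 1-month post-stroke" and discharge from hospital, but not current therapy, and recruitment includes support groups. The number in therapy may be below 10; the documents do not allow it to be estimated.

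**Step 7: which therapies.** Section 1.0 refers to rehabilitation activities, Section 4.0 names both outpatient speech therapy and rehabilitation therapy, and the Session 6 text names only speech therapy. This is a separate editorial matter, but a baseline item cannot match the Session 6 item until it is settled.

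**The case against.** The strongest reply is that a quantitative standard is being applied to a qualitative item. The plan consistently labels it so, analyses it for themes, and uses it to refine the intervention. Exploratory qualitative data on a possible effect is a legitimate choice in a pilot. Table 1 is hedged, and the Section 4.0 sentence speaks of good rather than better retention, which describes a level. All of this stands, and it is why the Section 4.0 sentence needs little change. It does not reconcile the comparative wording in Sections 1.0 and 10.0 with a single on-study report.

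A second reply is that the instruments are not reproduced. The speech therapy history taken at screening might capture enrolment, and the interviews might elicit change. This also stands, so the point is limited to what is described. The history item is not described as measuring attendance or adherence, and no comparison uses it.

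A third reply is that a baseline would add little, because the change would be recall-based, imprecise and uncontrolled. That limits what could be claimed. It does not remove the value of having a reference level for a stated hypothesis.

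A reader might also infer that a planned paired test has no baseline to work with, since the questionnaire appears under Secondary Outcomes and Section 12.0 plans paired *t*-tests for the secondary measures. The documents do not support that: Section 12.0 gives this questionnaire its own descriptive and qualitative analysis.

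**Conclusion.** The point holds on the documents as written. The plan can report how participants in therapy say they attended and followed recommendations during the study, and any change they perceive. It cannot say whether retention or adherence became better. This assumes that the unseen screening and interview instruments contain no structured earlier attendance or adherence items; none is described.

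The size is modest. This is one descriptive secondary item in a pilot aiming for 10 completers, and no planned test or sample size depends on it. A reader might infer that the gap weakens the trial's main conclusions. It does not: feasibility and acceptability are assessed separately, and the HADS has its own baseline and post-treatment values. Nor should a reader infer that a baseline would allow the change to be credited to the intervention, since there is no control group. The change is a cheap improvement that should be made, preferably before enrolment, because an unrecorded baseline can be recovered later only by longer recall.

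**What to change.** **Preferred.**
- At Screening/Baseline, ask the same enrolment, attendance and home-programme/adherence items as at Session 6, and state the look-back period at each visit.
- Choose one scope, speech therapy or all rehabilitation therapies, and use it in Sections 1.0, 4.0 and 10.0.
- Update Tables 1 and 2.
- In Section 12.0, plan to report change descriptively with the number actually in therapy, and state that it is imprecise and cannot be attributed to the intervention without a control group.

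**Cost.** Probably a few extra minutes (a judgement, not a figure from the documents). The visit of about 2 hours already holds consent, personal history, the WAB-R, eight psychosocial and communication scales and a cognitive test. The answers would rely on recall by people with aphasia.

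**If baseline items are not added.** Reword Sections 1.0 and 10.0 and the Table 1 rationale to claim only self-reported retention and adherence during participation, together with perceived change. The Section 4.0 sentence on association needs at most a light edit. This costs only wording changes.

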**2.0 Background**

Aphasia is a language disorder that occurs in about one-third of stroke survivors and affects the ability to speak, listen, read, and/or write. Aphasia can have devastating effects on functional communication and quality of life. Consequently, stroke survivors with aphasia are at much higher risk for depression than stroke survivors without aphasia. Approximately 70% of stroke survivors with aphasia experience depression post-stroke (Kauhanen et al., 2000), whereas only about one-third of the broader stroke population experience depression after their stroke (Mitchell et al., 2017). Anxiety disorders are also common in aphasia with prevalence estimated at 44% (Morris et al., 2017). Moreover, psychosocial problems like depression and anxiety negatively affect aphasia rehabilitation outcomes (Fucetola et al., 2006) and quality of life post-stroke (Ayerbe et al., 2014; Donnellan et al., 2010) likely, in part, due to low retention in and adherence to rehabilitation activities.

Despite this high prevalence of mental health issues in people with aphasia, their mental health needs are not being met (Baker et al., 2021; Strong & Randolph, 2021). One reason for this problem is that there are not many psychological interventions that have been adapted for people with aphasia and experimentally validated for this population (Baker et al., 2018). Traditional psychological interventions are heavily language-based making them less accessible to people with aphasia. The stepped care model for psychological care after stroke described by Kneebone (2016) is a framework proposed in the United Kingdom (UK) to target mental health problems in patients based on their individual needs. All stroke survivors enter Level 1 of the stepped care model, which is meant to prevent emotional problems. At Level 1, patients receive screening/assessment for psychosocial issues, psychoeducation, goal setting, problem solving, and monitoring of mood. Patients are moved up to Levels 2-4, depending on their diagnosis (Level 2: mild-moderate psychosocial impairment, Level 3: moderate-severe symptoms, Level 4: severe symptoms with challenging behaviors). Within this framework, patients may receive interventions at Levels 1 and 2 by non-mental health professionals, including SLPs or other paraprofessionals (Montgomery et al., 2010; Ryan et al., 2019). A systematic review examining interventions that target psychosocial wellbeing in post-stroke aphasia identified psychological interventions that fit within Levels 1 and 2 of the stepped care model that may be appropriate for people with aphasia (Baker et al., 2018). However, because the included studies examined stroke patients with and without aphasia within the same sample, it was unclear to what degree the subpopulation of people with aphasia benefited from these interventions. Furthermore, whether these interventions could feasibly be implemented by SLPs was not addressed. SLPs are uniquely positioned to be a “first-responder” to people with aphasia’s mental health needs given their expertise in communication and their understanding

of the impact of aphasia on mental health and daily life (Ryan et al., 2019). Specifically, equipping SLPs with the skills to address psychosocial needs in people with aphasia at Levels 1 and 2 of the stepped care model could have a substantial impact on patient psychosocial and rehabilitation outcomes. However, of the few studies that have examined psychosocial interventions for people with aphasia, some are not meant to be administered by SLPs (Thomas et al., 2012), and all require sessions that are 1-2 hours in length (Ryan et al., 2017; Thomas et al., 2012; Thomas et al., 2019). Furthermore, to our knowledge, no SLP-administered psychosocial interventions for PWA have been tested in the United States. Given the state of the health system in the United States, a psychosocial intervention that requires several weeks of 1-2 hour sessions is unlikely to be feasibly implemented as part of standard clinical practice. Therefore, there is a need for a shorter intervention that SLPs can feasibly implement into their clinical practice with their patients with aphasia. Communication and collaboration of SLPs with mental health professionals is vital for the development of such an intervention. Therefore, a team-based approach to developing and testing a psychosocial intervention for people with aphasia to be administered by SLPs is essential. Our project will address this gap by testing an SLP-administered psychosocial intervention in a sample of people with aphasia that is designed collaboratively by an SLP and clinical psychologist. Intervention sessions are designed to be about 30 minutes, and thus, potentially more feasible for clinicians if it is found to be effective.

### 3.0 Intervention to be studied

Included participants with aphasia will engage in weekly sessions of an SLP-administered psychosocial intervention for 8 weeks. Activities to be completed throughout the intervention are outlined in detail below. Throughout the intervention, supported communications strategies will be used to facilitate communication with people with aphasia, according to their communication needs/aphasia severity.

The psychosocial intervention includes psychoeducation, behavioral activation therapy, education on sleep hygiene, and relaxation training. Psychoeducation has been shown to be effective at improving the clinical course, treatment adherence, and psychosocial functioning of depressed patients (Souza Tursi et al., 2013). In stroke, specifically, psychoeducation has been shown to improve functional outcomes of patients, reduce caregiver burden, and improve stroke survivors' quality of life (Cheng et al., 2018; Mou et al., 2021). Behavioral activation therapy is rooted in the idea that depression and low mood arise from a lack of reinforcement from the environment and the activities that one partakes in. Behavioral activation therapy has been shown to be an effective treatment for depression in adults (Chan et al., 2017; Mazzucchelli et al., 2009; Pinquarti et al., 2007; Scogin et al., 2005; Soucy Chartier & Provencher, 2013), comparable to the effects of cognitive behavioral therapy in treating depression (Cuijpers et al., 2013; Richards et al., 2016). It has also been tested in the UK with people with aphasia and has been shown to be effective and appropriate for this population as it does not rely as heavily on verbal communication as other approaches (Thomas et al., 2013; Thomas et al., 2019). Stroke survivors are at risk for sleep disturbances and poor quality of sleep (Zhao et al., 2022), which can affect their cognitive and psychosocial functioning. Education on sleep hygiene as part of stroke education may result in higher sleep quality and quality of life (Urcan & Kolcu, 2022). Finally, relaxation training has been shown to be an appropriate intervention for people with aphasia (El-Helou et al., 2022; Ryan et al., 2020) and has been shown to be effective in reducing post-stroke anxiety (Golding et al., 2015) and potentially an effective adjuvant to language therapy (Marshal & Watts, 1976; Murray & Ray, 2001).

Below we outline what will occur in each intervention session with participants.

**Intervention Session 1:** Session 1 will last approximately 30 minutes and focus on psychoeducation and an introduction to behavioral activation therapy. Session agenda:

- **Assessments (5 minutes):**
  - Hospital Anxiety and Depression Scale (HADS; Zigmond & Snaith, 1983)
  - Dynamic Visual Analog Mood Scale (D-VAMS; [http://dvams.com/dvams/menu\\_home\\_dvams.htm](http://dvams.com/dvams/menu_home_dvams.htm); Barrows, 2013)
  - Simple Aphasia Stress Scale (SASS; Laures-Gore & Rice, 2019)
- Participants will receive psychoeducation focused on (10 minutes):
  - normalizing the participant's psychosocial symptoms (e.g., loss of identity, depression, anxiety) and emotions (e.g., grief, anger, guilt, fear, embarrassment, etc.), which are common after stroke.
  - Discuss common effects of stroke/aphasia on daily life (e.g., social isolation, relationships, work, daily activities).
  - Discuss ways that depression, anxiety, or low mood can affect rehabilitation (e.g., attendance, homework completion, low engagement/motivation, perhaps less neuroplasticity)
- Participants will be introduced to the concept of behavioral activation therapy and the goal to increase the number of enjoyable activities that the participant partakes in. Participants will be asked what types of activities they enjoyed before their stroke, the activities/roles in their lives that they value, and the barriers they've faced to engaging in these activities. A list will be started of activities they enjoy/value and used throughout the intervention. (15 minutes)
- **Homework:** activity monitoring for participants to track how they currently spend their time and their mood during each activity with the help of a care partner if available.

**Intervention Session 2:** This session will last about 35 minutes and will consist of ongoing behavioral activation therapy and education on sleep hygiene.

- Assessments: HADS, D-VAMS, SASS (5 minutes)
- The SLP will go over the activity monitoring assignment with the participant and schedule valued/prefereed activities with the participant for the following week. Participants and the SLP will collaboratively problem solve as concerns about ability to engage in preferred activities arise. (20 minutes)
- The SLP will educate the participant on the importance of sleep and sleep hygiene practices that can improve sleep. The SLP will suggest ways the participant can instill proper sleep hygiene into their routine. (10 minutes)
- **Homework:** 1) engage in scheduled activities, 2) track mood after activities and take note of difficulties that arose in completing the activity, and 3) choose/implement one method for improving sleep hygiene.

**Intervention Session 3:** This session will last about 30 minutes and will consist of ongoing behavioral activation therapy and relaxation training.

- Assessments: HADS, D-VAMS, SASS (5 minutes)

- The SLP will go over the participant's homework to determine whether they completed the preferred activities and sleep hygiene homework. The SLP and participant will collaboratively problem solve to increase participation in these activities. Additional activities will be scheduled for the following week. (15 minutes)
- The SLP will educate the participant on relaxation techniques, including deep breathing, positive visualization, progressive muscle relaxation, mindfulness techniques, and phone/tablet applications or websites that may help with this practice. (10 minutes)
- **Homework:** 1) engage in scheduled activities with tracking, and 2) choose/implement one method for relaxation.

**Intervention Sessions 4:** These sessions will last about 30 minutes and will consist of ongoing behavioral activation therapy.

- Assessments: HADS, D-VAMS, SASS (5 minutes)
- The SLP will go over the participant's homework to determine whether they completed the preferred activities and relaxation training homework. The SLP and participant will collaboratively problem solve to increase participation in these activities. Additional activities will be scheduled for the following week. (20 minutes)
- **Homework:** 1) engage in scheduled activities with tracking

**Intervention Session 5:** This session will last about 30 minutes and will consist of ongoing behavioral activation therapy and planning for maintenance of activities.

- Assessments: HADS, D-VAMS, SASS (5 minutes)
- The SLP will go over the participant's homework to determine whether they completed the preferred activities. The SLP and participant will collaboratively problem solve to increase participation in these activities without the weekly accountability. Additional activities will be scheduled for the following week. (20 minutes)

**Three weekly booster phone calls:** After the five intervention sessions and post-treatment assessments, we will conduct three weekly phone calls to discuss behavioral activation activities and problem solve any issues participants are having with completing pleasant/scheduled activities. These weekly phone calls will occur between the post-treatment assessment session and the 1-month follow-up session.

